7.1.3. Recording an Adverse Event

All AEs/SAEs will be entered into the electronic database.

Planned hospital admissions or surgical procedures for an illness or disease that existed before the subject was enrolled in the study are not to be considered AEs unless they occur at a time other than the planned date or the pre-existing illness or disease worsens after enrollment into the study.

Fractures identified during the study are not to be recorded as AEs unless the subject is hospitalized, the fracture is complicated, or the Investigator considers the fracture to be unrelated to the subject's underlying osteoporosis. All fractures will be identified and evaluated as part of the disease assessment and will be documented in the CRF and by collection of source documents.

For both serious and non-serious AEs, the Investigator must determine the intensity of the event and the relationship of the event to study drug administration (abaloparatide and placebo). Intensity for each AE will be defined according to the following criteria:

Intensity	Definition
Mild	Awareness of sign or symptom, but easily tolerated.
Moderate	Discomfort enough to cause interference with normal daily activities.
Severe	Inability to perform normal daily activities.

If the intensity of an adverse event changes within a day, the maximum intensity should be recorded. If the intensity changes over a longer period of time, the changes should be recorded as separate events (having separate onset and stop dates for each intensity).

Relationship to blinded study drug administration will be determined by the Investigator according to the following criteria:

Relationship	Definition
None	No relationship between the event and the administration of study drug. The event is related to other etiologies, such as concomitant medications or subject's clinical state.
Unlikely	The current state of knowledge indicates that a relationship to study drug is unlikely or the temporal relationship is such that study drug would not have had any reasonable association with the observed event.
Possible	A reaction that follows a plausible temporal sequence from administration of the study drug and follows a known response pattern to the suspected study drug. The reaction might have been produced by the subject's clinical state or other modes of therapy administered to the subject.

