#### 4.5.3 Adverse Events

All adverse events (AEs) will be coded by System Organ Class (SOC) and Preferred Term (PT) using the MedDRA (Version 24.0) coding system. Analyses of AEs will be performed for those events that are considered to be Treatment-Emergent Adverse Events (TEAEs). A TEAE is defined as any AE that was absent (i.e., had not occurred) or had resolved prior to the start of

study drug, and which occurred on or after the date of the first dose of study drug and within 30 days of the last dose of study drug; or any AE that started prior to the first dose of study drug, was ongoing after study treatment started, and increased in severity after the start of study drug and within 30 days of the last dose of study drug. AEs with missing onset dates will be handled according to the Conventions for Imputing Missing Dates in Appendix D.

In any tabulation of adverse events, a subject contributes only once to the count for a given SOC or PT. For summaries by severity, a subject with multiple occurrences of an AE will be represented under the most severe occurrence. For summaries by relationship to study drug, a subject with multiple occurrences of an AE will be represented under the most related occurrence.

An overall summary of the adverse events will be provided, in which the number of subjects with any adverse events, number of subjects with any TEAEs, number of subjects with any treatment-related TEAEs, number of subjects with any severe TEAEs, number of subjects with any treatment-related severe TEAEs, number of subjects with any serious TEAEs, number of subjects with any TEAES leading to study drug withdrawal, number of subjects with any TEAEs leading to study drug interruption, number of subjects with any TEAEs leading to study discontinuation, and number of subjects with any TEAEs leading to death will be summarized by treatment groups.

The following summaries will also be presented:

- TEAEs by SOC and PT
- TEAEs by SOC, PT, and region (North America and Europe)
- TEAEs by PT. Note: TEAEs will be sorted in descending order of total number of subjects with the preferred term in the abaloparatide-SC treatment group
- TEAEs by SOC, PT, and maximum severity
- Severe TEAEs by SOC and PT
- Treatment-related severe TEAEs by SOC and PT
- TEAEs by SOC, PT, and relationship to study drug
- Treatment-related TEAEs by SOC and PT
- TEAEs leading to study drug interruption by SOC and PT
- TEAEs leading to study drug withdrawal by SOC and PT

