- TEAEs leading to study discontinuation by SOC and PT
- TEAEs leading to death by SOC and PT
- Serious TEAEs by SOC and PT
- Treatment-related serious TEAEs by SOC and PT
- Most common (>=5% in any treatment group) TEAEs by SOC and PT
- Non-TEAEs by SOC and PT

SOCs will be sorted in alphabetical order. Within an SOC, AEs will be sorted in descending order of the total number of subjects with the preferred term in the abaloparatide group.

To explore the relationship between TEAEs and the duration of study drug exposure, the incidence of TEAEs by time of onset ( $\leq 1$  month,  $1 < to \leq 3$  months,  $3 < to \leq 6$  months,  $6 < to \leq 9$  months, and >9 months) will be summarized by treatment group, SOC and PT. Subjects with multiple occurrences of an AE within a time period will be counted once in each time period that an onset of the AE occurs.

To evaluate the relationship between TEAEs and the antibody status, the incidence of TEAEs will be summarized by antibody status (ADA-, ADA+/Nab+, ADA+/Nab-, All ADA+, and Overall), SOC, and PT using the Antibody Population. A summary of TEAEs by PT and antibody status will also be presented, in which TEAEs will be sorted in descending order of total number of subjects with the preferred term in the overall abaloparatide-SC treatment group.

During the COVID-19 pandemic, AEs may be assessed through phone/video by the investigator conducting the study visit with subjects remotely. To explore the effect of the COVID-19 pandemic on reported AEs, summaries of TEAEs by SOC and PT, TEAEs leading to treatment discontinuation, and serious TEAEs will also be presented:

- by subject's study status relative to COVID-19 pandemic onset (subjects who completed or withdrew from the study before 01 March 2020, vs subjects who completed or withdrew from the study on or after 01 March 2020)
- by AE onset dates relative to COVID-19 pandemic onset (AE occurs before 01 March 2020, vs AE occurs on or after 01 March 2020)
- by region (North America and Europe)

The number of subjects with any TEAEs, the number of subjects with any SAEs, and the number of subjects with TEAEs leading to study drug withdrawal will also be summarized by treatment group, SOC, PT and age group (< 65, 65 - < 75, and  $\ge$  75 years). Similar tables will be provided by treatment group, SOC, PT and BMI group (BMI < 25, 25  $\le$  BMI < 30, and BMI  $\ge$  30).

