## **Adverse Events of Special Interest**

An adverse event of special interest (AESI) is an AE that is designated to be of special medical or scientific interest to the Sponsor. There are four major categories of AESIs as follows:

- Injection site reaction AEs -- Skin reaction AEs at the injection site
- Skin AESIs -- AEs of eschar, ulcer, or non-healing wounds at the injection site
- Hypersensitivity AESIs -- TEAEs in the Hypersensitivity Standardized MedDRA Query (SMQ narrow)
- Other AESIs:
  - Orthostatic hypotension

Study BA058-05-019 SAP

- Tachycardia
- Nausea
- Hypercalcemia
- Hypercalciuria
- Hypophosphataemia

The MedDRA PTs, High Level Terms (HLT), and SMQs used to identify the AESIs are stored in the study folder in the Biometrics SAS Environment.

An overall summary of the treatment emergent AESIs will be provided, in which the number of subjects with any adverse events, number of subjects with any TEAEs, number of subjects with any treatment-related TEAEs, number of subjects with any severe TEAEs, number of subjects with any treatment-related severe TEAEs, number of subjects with any serious TEAEs, number of subjects with any treatment-related serious TEAEs, number of subjects with any TEAES leading to study drug withdrawal, number of subjects with any TEAEs leading to study drug interruption, number of subjects with any TEAEs leading to study discontinuation, and number of subjects with any TEAEs leading to death will be summarized by treatment group.

The treatment emergent AESIs will be summarized by PT and SOC for each of the AESIs. Summary of the onset time and duration of the treatment emergent AESIs will be provided by treatment group using descriptive statistics (number of subjects, mean, SD, median, interquartile range, minimum and maximum). The number of subjects in each of the onset time groups (1 day, 2-3 days, 4-7 days, 8-15 days, 16-29 days, 1 to <2 months, 2 to <6 months, 6 to <10 months, and >=10 months) and duration groups (1 day, 2-3 days, 4-7 days, 8-15 days, 16-29 days, and >= 30 days) will also be summarized by treatment group.

To evaluate the relationship between AESIs and the antibody status, the incidence of treatment emergent AESIs will also be summarized by antibody status (ADA-, ADA+/Nab+, ADA+/Nab-, All ADA+, and Overall), SOC, and PT for the abaloparatide SC group.

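### A continuing AE is split into new records at each intensity change, and the SAP time-of-onset table counts those records as fresh onsets because nothing links them

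*Protocol*

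**What the plan says.** Protocol 7.1.3 has two recording rules. Within one day: "If the intensity of an adverse event changes within a day, the maximum intensity should be recorded". Beyond one day: "If the intensity changes over a longer period of time, the changes should be recorded as separate events", each with its own onset and stop date. The second rule does not distinguish worsening from improvement.

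SAP 4.5.3 plans a table of "the incidence of TEAEs by time of onset", in five periods (up to 1 month, then to 3, 6 and 9 months, and beyond 9). Its stated purpose is to explore how TEAEs relate to the duration of exposure. In that table a subject with repeated occurrences "will be counted once in each time period that an onset of the AE occurs".

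For adverse events of special interest (AESIs), the SAP adds: "Summary of the onset time and duration of the treatment emergent AESIs will be provided by treatment group using descriptive statistics". It also gives numbers of subjects in onset-time groups and in duration groups that run from 1 day to 30 days or more.

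Two general rules in SAP 4.5.3 apply to AE tables. A subject counts once per system organ class or preferred term, and severity summaries use the most severe occurrence.

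**The concern.** The protocol defines a record by intensity. The time-of-onset table needs a record defined by the start of an event. With no step between them, a reaction that begins early and later eases produces a second onset date, and the table counts it in the later period if that date falls there. A reader would take this as an event newly arising after months of treatment, when it is an old event getting better. That bears on the exposure question the table is meant to explore.

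The AESI summaries have a related gap. If a man has three contiguous records of one reaction, the SAP does not say which onset date or which duration represents him. How long an AESI lasted would then depend on an undocumented programming choice.

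**Working it through.** The plan states no figure on this point, so there is nothing to reproduce. The check sets the rules side by side, applies them literally to examples, and then shows a range under stated assumptions.

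**Step 1. Is there any linking step?**

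| Rule | Where | Effect on split records |
|---|---|---|
| New record at each intensity change beyond a day | Protocol 7.1.3 | One continuing AE becomes several records with later onsets |
| One count per subject per class or term | SAP 4.5.3 | Protects overall incidence |
| Most severe occurrence used | SAP 4.5.3 | Protects maximum-severity tables |
| One count in every period with an onset | SAP 4.5.3, time-of-onset table | Protects within a period, not across periods |
| AESI onset time and duration | SAP 4.5.3, AESI part | No episode defined; which record represents the subject is not stated |
| Partial-date rules | SAP Appendix D | Impute dates; do not join records |

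No rule links or merges consecutive records of the same AE.

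**Step 2. Literal application.** One month is 30 days (Protocol 6.2), so the periods end on Days 30, 90, 180 and 270. Duration = stop − onset + 1. The episodes are invented illustrations.

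| Episode | Change on Day | Record durations | Periods counted, as written | First onset | Episode duration |
|---|---|---|---|---|---|
| A: Days 20–200 | 95, 130 | 75, 35, 71 | up to 1 month; 3–6 months | up to 1 month | 200 − 20 + 1 = 181 |
| B: Days 25–50 | 35, 41 | 10, 6, 10 | up to 1 month; 1–3 months | up to 1 month | 50 − 25 + 1 = 26 |
| C: Days 20–300 | 280 | 260, 21 | up to 1 month; over 9 months | up to 1 month | 300 − 20 + 1 = 281 |
| D: Days 100–160 | 130 | 30, 31 | 3–6 months only | 3–6 months | 160 − 100 + 1 = 61 |

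A, B and C each gain a count in a later period. D does not, because its change stays inside one period. The overstatement therefore needs a change that crosses a boundary.

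On duration, any single record is shorter than its episode. The band may or may not be wrong. In A every record still falls in the group of 30 days or more. In B every record falls in the 4–7 or 8–15 day group, while the episode belongs in 16–29.

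**Step 3. Possible size, under assumptions only.** The documents give neither the share of AEs that change intensity nor AE length. A simulation assumed exponential onset with mean 60 days, at most one change at a uniformly distributed time, and follow-up to Day 390.

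| Assumed mean AE length | Changed AEs that cross a period boundary | Factor on incidence beyond 9 months if 5% / 15% / 30% of AEs change |
|---|---|---|
| 10 days | about 9% | 1.01 / 1.02 / 1.04 |
| 60 days | about 39% | 1.09 / 1.27 / 1.53 |
| 180 days (about 150 after the follow-up limit) | about 63% | 1.59 / 2.77 / 4.59 |

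The large factors act on a small base: about 0.9% of simulated AEs truly begin after month 9, and the most extreme case raises this to 3.93%. The simulation does not separate worsening from improvement, so it overstates the part due to improvement alone.

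**The case against.** The strongest reply is that the main safety outputs are sound. The once-per-subject and most-severe rules protect overall incidence and maximum severity. Safety analyses are descriptive, and the onset table is exploratory. Several AESIs also have summaries that do not use AE records: local tolerance (SAP 4.5.5), hypercalcemia and hypercalciuria (4.5.6), orthostatic hypotension (4.5.7) and heart-rate increase (4.5.7, 4.5.8). All of this stands, and it limits the weight of the point. It does not answer it for the time-of-onset table, which has its own explicit counting rule.

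A reader might infer four stronger things that the documents do not support.

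- **That the SAP understates AESI duration.** The SAP tabulates numbers of subjects and does not say that each record contributes its own duration. A programmer could join the records, or use the longest. The defect is a missing definition. A percentage shrinkage in mean duration would need per-record tabulation and a rate of grade change, and neither is in the documents.
- **That a pre-dose event which only improves becomes treatment-emergent.** The first part of the TEAE definition requires an AE that was absent or resolved before study drug and "which occurred on or after the date of the first dose of study drug". The second part requires increased severity. An ongoing event that eases meets neither, unless each record is read as a new AE. The split records invite that misreading, but the plan does not prescribe it.
- **That the distortion is larger in the active arm.** Neither document gives rates of grade change by arm. More reactions in one arm would not in themselves mean that a larger share of them change grade.
- **That overall incidence or severity is biased.** The general counting rules largely prevent this.

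**Conclusion.** The point holds for the time-of-onset table. The protocol's recording rule and the SAP's counting rule, followed literally, count a continuing or improving AE as a later onset whenever a grade change crosses a period boundary. The direction follows from the text: later-period incidence can only be raised. The size cannot be derived; the simulated factors run from 1.01 to 4.59 and rest wholly on the assumed inputs.

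For AESIs the finding is narrower. Onset time and duration are undefined when a man has several contiguous records, and taking any single split record would understate the duration.

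No efficacy result is affected. This is a gap to close before database lock. It does not threaten the trial's main conclusions.

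**What to change.** Add to SAP 4.5.3:

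- Contiguous records of the same preferred term in a subject form one episode. Contiguous means that the next onset falls on the day of the previous stop or the day after.
- AESI duration runs from the first onset to the last stop of the episode.
- For the time-of-onset table and AESI onset time, a continuation record at the same or lower intensity is not a new onset. It is not treatment-emergent if the episode began before first dose.
- A record of increased intensity keeps its own date for TEAE status, including the worsening of a pre-dose event. Worsening of an on-treatment episode is shown separately from first onset.
- Severity tables and listings stay as recorded.

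Under this rule examples A, B and C each count once, in the first month, with durations of 181, 26 and 281 days; any worsening among the changes appears in the separate display.

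A simpler rule that gives every episode its first onset and maximum intensity should be avoided. It would back-date a late worsening to an early mild onset and give a pre-dose event that worsens on treatment a pre-dose onset, although the SAP treats such worsening as treatment-emergent.

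The cost is a few lines of text and one derivation, with no new data collection. The small downside is that a true recurrence starting the day after resolution would be merged with the first episode.

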7.1.3.1. Serious and Unanticipated Adverse Device Effects for Abaloparatide-SC

An adverse device effect (ADE) is defined as any adverse event related to the use of an investigational medical device (IMD). For the purposes of this protocol, abaloparatide-SC is the IMD. All ADEs should be reported as an AE per Section 7.1, which includes AEs resulting from insufficient or inadequate instructions for use, deployment, implantation, installation, operation, any malfunction of the IMD, use error, or intentional misuse of the IMD (ISO/DIS 14155).

An unanticipated adverse device effect (UADE) is defined as any serious adverse effect on health or safety or any life-threatening problem or death caused by, or associated with, the abaloparatide-SC device, if that effect, problem, or death was not previously identified in nature, severity, or degree of incidence in the application/IB, or any other unanticipated serious problem associated with a device that relates to the rights, safety, or welfare of subjects (21 CFR 812.3(s)).

Any UADE that occurs during the study from the time the subject signs the ICF until 30 days after the last dose of study medication must be reported within 24 hours of first awareness of the event using the SAE and the UADE report forms and emailing to [contact].

The Investigator and the Sponsor will immediately conduct an evaluation of any UADE occurring with abaloparatide-SC. The results of the evaluation will be reported to the IRB within 10 days of the Sponsor becoming aware of the event.

If it is determined by the Investigator and the Sponsor to present an unreasonable risk to study subjects, all investigations or parts of the investigation presenting that risk will be terminated as soon as possible. Termination will occur not later than 5 working days after the Investigator and the Sponsor makes this determination and not later than 15 working days after the Sponsor first receiving notice of the event. The Investigator and the Sponsor will not resume an investigation terminated under these conditions without an additional IRB approval.

7.1.4. Serious Adverse Event Reporting

Any SAEs that occur during the study from the time the subject signs the ICF until 30 days after the last dose of study medication must be reported within 24 hours of first awareness of the event using the SAE report form and emailing to [contact]. Data should also be entered in the clinical trial eCRF.

Treatment-related SAEs will be followed until resolution or stabilization. The reference safety information for this study is the IB, which will be provided under separate cover to all Investigators.

Any SAEs that occur at any time after completion of the study, which the Investigator considers to be related to study drug, must be reported to the Sponsor or its designee.

The Investigator must submit the SAE to the IRB/ IEC in accordance with 21 CFR parts 56 and 312 as well as with applicable local regulations. Documentation of these submissions must be retained in the site study file.

7.1.5. Device Reporting

Abaloparatide-SC is a drug-device combination product. In order to fulfill regulatory reporting obligations worldwide, the Investigator is responsible for the detection and documentation of events meeting the definition of a UADE that occurs with abaloparatide-SC (Section 7.1.3.1).

Any UADEs that occur during the study with abaloparatide-SC, from the time the subject signs the ICF until 30 days after the last dose of study drug, must be reported within 24 hours of first awareness that the event meets the definition of a reportable incident by entering data in the clinical trial eCRF. Treatment-related UADEs will be followed until resolution or stabilization, the condition is otherwise explained, or until the subject is lost to follow-up.

SAEs (initial reports and follow-up information) must be reported by the Investigator using the SAE report form; the form must be completed and emailed to [contact].

The Investigator will comply with the applicable local regulatory requirements relating to reporting to the IRB/IEC.

7.1.6. Follow-up of Adverse Events

All treatment-related AEs will be followed with appropriate medical management until resolved or stabilized.

UADEs will be followed until their medical outcome is determined, with periodic written reports about the status provided to the Sponsor.

7.1.7. Abuse, Misuse, Overdose, or Medication Error

Abuse, misuse, overdose, or medication error (as defined below) must be reported to the Sponsor whether or not they result in an AE/SAE.

- Abuse Persistent or sporadic intentional intake of investigational medicinal product at a dose higher than prescribed per protocol (but below the dose defined for overdose) or when used for non-medical purpose (e.g., altering one's state of consciousness).
- Misuse Intentional or unintentional use of investigational medicinal product other than as directed or indicated at any dose, which is at or below the dose defined for overdose Note: this includes a situation where the test article is not used as directed at the dose prescribed by the protocol.
- Overdose Intentional or unintentional injection of a dose of abaloparatide at least 2 times higher than the protocol-specified dose and is associated with clinical symptoms.
- Medication Error A mistake made in prescribing, dispensing, administration and/or use of the investigational medicinal product.

